Adverse effects that may be associated with LACTIN-V include those seen with other vaginally administered products, and include:

Most likely:

- Vaginal, genital or menstrual symptoms: vaginal discharge

Less likely:

- Gastrointestinal symptoms: abdominal (stomach area) pain, constipation, diarrhea, nausea, vomiting
- Urinary symptoms: needing to urinate urgently, needing to urinate at night and pain with urination
- Vaginal, genital or menstrual symptoms: genital itching, bleeding between menstrual periods, delayed menstrual periods, vaginal odor, vaginal burning sensation, vaginal irritation, vaginal bleeding, vaginal dryness, genital swelling, rash, vaginal candidiasis (yeast infection)
- Other symptoms: lower back pain

Rare but potentially life-threatening:

- Allergic reaction (including anaphylaxis) to the study product

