6. GENERAL STATISTICAL CONSIDERATIONS

6.1. General Principles

Tabulations will be used extensively to summarize the data. All continuous variables will be summarized using the following descriptive statistics: n (sample size), mean, standard deviation, median, maximum, and minimum. The frequency and percentages (based on the sample size) of observed levels will be reported for all categorical measures. Wilson confidence intervals for binomial proportions and differences in binomial proportions will be computed for efficacy variables. Blaker confidence intervals for binomial proportions and differences in binomial proportions will be computed for safety variables. For the hypothesis tests comparing treatment groups with respect to safety outcomes, the two-sided Fisher's Exact test will be used. For the hypothesis tests comparing treatment groups with respect to efficacy outcomes, the two-sided Chi-Square test will be used. For all tests, a 5% two-sided significance level will be used.

For all efficacy outcome measures, the Complete Case population (see Section 6.3) will be used as the primary analysis population and the Per Protocol, modified Intent-to-Treat, and Intent-to-Treat populations will be used as secondary analysis populations. For all safety analyses, the Safety population will be used as the analysis population.

All summary tables will be structured with a column/sub-table for each treatment group (LACTIN-V, Placebo, and All Subjects). In general, all data will be listed by treatment group and/or subject, and when appropriate by visit number within subject. The total population size relevant to that table/column if applicable, including any missing observations will be displayed in the tables.

Note that in the data listings, Subject ID is the unique subject identifier, not the Study ID used on study and dates will not be included, only Study Day. Study Day 1 will be the day of the first dose of treatment.

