9.7. Vital Signs and Physical Evaluations

A complete physical examination, assessment of vital signs, and a pelvic examination will be performed at screening and symptom-directed examinations will be performed at all subsequent visits. Vital sign measurements include systolic blood pressure, diastolic blood pressure, pulse, respiration, oral temperature, height, and weight. Since the evaluations are symptom-driven from enrollment to the end of follow-up, subject listings will be provided for vital signs ([Listing 29](#)), physical exam findings ([Listing 30](#)), and pelvic exam findings ([Listing 31](#)). Abnormal discharge and cervical mucus characteristics are displayed by visit and treatment group in [Table 133](#), [Table 134](#), and [Table 135](#). Subject listings will be provided for abnormal discharge ([Listing 32](#)), and cervical mucus characteristics ([Listing 33](#)).

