	Yellow	x	x	x	x	x	x	x	x
	Brown	x	x	x	x	x	x	x	x
	Bloody	x	x	x	x	x	x	x	x
Consistency	Non-homogenous (normal)	x	x	x	x	x	x	x	x
	Homogenous	x	x	x	x	x	x	x	x
	Curdy/Plaques	x	x	x	x	x	x	x	x
	Frothy	x	x	x	x	x	x	x	x
	Other	x	x	x	x	x	x	x	x
Distribution	Pooled	x	x	x	x	x	x	x	x
	Diffuse	x	x	x	x	x	x	x	x
	Patches	x	x	x	x	x	x	x	x
Odor	None	x	x	x	x	x	x	x	x
	Foul	x	x	x	x	x	x	x	x
	Fishy	x	x	x	x	x	x	x	x
Cervical Mucus									
Amount	Minimal (to os)	x	x	x	x	x	x	x	x
	Moderate (on face)	x	x	x	x	x	x	x	x
	Profuse (pools)	x	x	x	x	x	x	x	x
Color	Clear	x	x	x	x	x	x	x	x
	Opaque White	x	x	x	x	x	x	x	x
	Translucent White	x	x	x	x	x	x	x	x
	Yellow	x	x	x	x	x	x	x	x
	Brown	x	x	x	x	x	x	x	x

All Subjects (N=X)									
Category	Value	Visit 1 (N=X)		Visit 2 (N=X)		Visit 3 (N=X)		Visit 4 (N=X)	
		n	%	n	%	n	%	n	%
	Bloody	x	x	x	x	x	x	x	x
Viscosity	Thin	x	x	x	x	x	x	x	x
	Average	x	x	x	x	x	x	x	x
	Thick	x	x	x	x	x	x	x	x

Note: Denominator for percentages are the number of subjects with abnormal discharge that can be evaluated at the respective visit

Tables with similar format:

Table 134: Abnormal Discharge and Cervical Mucus Characteristics by Visit and Treatment Group - Safety Population - LACTIN-V

Table 135: Abnormal Discharge and Cervical Mucus Characteristics by Visit and Treatment Group - Safety Population - Placebo

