Visit 2, Week 4 (Day 28)	xx	xx	xx	xx	xx	xx
Visit 3, Week 8 (Day 56)	xx	xx	xx	xx	xx	xx
Visit 4, Week 12 (Day 84)	xx	xx	xx	xx	xx	xx
Visit 7, Week 24 (Day 168)	xx	xx	xx	xx	xx	xx

Implementation Notes:

- Sort order is actual treatment group, Subject ID, Study Day.
- If all subjects received the correct treatment, only display “Treatment Group”.

Listing 30 Physical Exam Findings

Actual Treatment Group	Randomized Treatment Group	Subject ID	Study Day	Body System	Abnormal Finding	Reported as an AE? (AE Description; AE Number)
LACTIN-V/Placebo	LACTIN-V/Placebo	xxxxxxx	xxx	xxxxxxxxx	xxxxxxxxx	Yes/No xxxxxx; xx

Implementation Notes:

1. Sort order is actual treatment group, Subject ID, Study Day.
2. If all subjects received the correct treatment, only display “Treatment Group”.
3. Only abnormal findings will be presented.
4. If the physical exam was reported as an AE, then concatenate the Physical exam with the Adverse Events by AENUM and report the AETERM, plus the AE Number

Listing 31 Pelvic Exam Findings

Actual Treatment Group	Randomized Treatment Group	Subject ID	Study Day	Body System	Abnormal Finding	Reported as an AE? (AE Description; AE Number)
LACTIN-V/Placebo	LACTIN-V/Placebo	xxxxxxx	xxx	xxxxxxx	xxxxxxx	Yes/No xxxxxx; xx

Implementation Notes:

1. Sort order is actual treatment group, Subject ID, Study Day.
2. Only abnormal findings will be presented.
3. If the pelvic exam was reported as an AE, then concatenate the Pelvic exam with the Adverse Events by AENUM and report the AETERM, plus the AE Number
4. If all subjects received the correct treatment, only display “Treatment Group”.

Listing 32 Abnormal Discharge

Study Day	Does the subject have abnormal discharge that can be evaluated?	Source of Discharge	Amount of Discharge	Discharge Character	Discharge Color	Discharge Consistency	Discharge Distribution	Discharge Odor
Actual Treatment Group: , Randomized Treatment Group: , Subject ID:								
xx	Yes/No	Vagina/Cervix	Minimal/Moderate/Profuse	Thin watery/ Normal/Thicker than normal	White/Clear/Yellow/Brown/Bloody	Non-homogenous (normal/homogenous/ Curdy plaques/Frothy/Other	Pooled/Diffuse/Patches	None/foul/fishy

Implementation Notes:

1. Sort order is Actual treatment group, Subject ID, Study Day.
2. If all subjects received the correct treatment, only display “Treatment Group”.

Listing 33 Cervical Mucus

Actual Treatment Group	Randomized Treatment Group	Subject ID	Study Day	Amount	Color	Viscosity

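### Tables 133-135 divide the cervical mucus rows by women with abnormal discharge, and omit the clinician-observed discharge frequency and Visit 7

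*SAP*

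**What the plan says.** SAP 9.7 plans three tables from the pelvic examination: "Abnormal discharge and cervical mucus characteristics are displayed by visit and treatment group". It names no denominator. The shell for Table 133 (SAP Appendix 1) has two blocks. The first gives source, amount, character, color, consistency, distribution and odor of abnormal discharge. The second gives amount, color and viscosity of cervical mucus. One footnote covers both: "Denominator for percentages are the number of subjects with abnormal discharge that can be evaluated at the respective visit". Tables 134 and 135 repeat the format for each arm, for example "Table 134: Abnormal Discharge and Cervical Mucus Characteristics by Visit and Treatment Group - Safety Population - LACTIN-V". The columns are Visits 1 to 4, each headed by an N that is not defined.

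The subject-level sources are separate. Listing 32 opens with a Yes/No item, "Does the subject have abnormal discharge that can be evaluated", and then gives the discharge characteristics. Listing 33 gives mucus amount, color and viscosity, and has no such item.

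Protocol 2.3.1.1 places one entry under its most likely adverse effects: "Vaginal, genital or menstrual symptoms: vaginal discharge".

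**The concern.** The footnote fits only one of the two blocks. Mucus is not described only in women with abnormal discharge: its categories include ordinary values such as clear color and average viscosity. A percentage of mucus findings over women with discharge therefore has no useful meaning.

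Two further gaps sit in the same shell. The Yes/No discharge item defines the denominator but is not itself reported, so no printed percentage says how many examined women had abnormal discharge. Visit 7 has no column, although Protocol 7.8 includes a pelvic examination at that visit and the safety objective runs to 24 weeks.

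At stake is the by-arm, by-visit summary of an examination finding for the reaction that the protocol expects most. SAP 9.7 sends the other pelvic findings to listings only.

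**Working it through.** The plan states no figure for this point, so there is none to reproduce. The documents also give no rates for clinician-observed discharge or mucus categories; the rates below are assumptions and are shown as a range.

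**Inputs.** SAP 5 gives 228 women at 2:1, hence 228 × 2/3 = 152 on LACTIN-V and 228 × 1/3 = 76 on placebo. All are taken as attending the visit, for illustration.

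**Step 1: mucus rows, all women with mucus data counted.** Let m be the share of attenders in a mucus category and d the share with evaluable abnormal discharge. The shell prints 100 × m/d, which exceeds 100% whenever m > d. With m = 50% (76 of 152 women; 38 of 76 women) and discharge counts rounded to whole women:

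| d | LACTIN-V, 152 women | Placebo, 76 women |
|---|---|---|
| 10% | 76/15 = 507% | 38/8 = 475% |
| 20% | 76/30 = 253% | 38/15 = 253% |
| 40% | 76/61 = 125% | 38/30 = 127% |
| 60% | 76/91 = 84% | 38/46 = 83% |
| 80% | 76/122 = 62% | 38/61 = 62% |

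With m = 30% in 152 women (46 women), the values are 46/15 = 307%, 46/30 = 153% and 46/61 = 75% at d = 10%, 20% and 40%. Passing 100% is therefore possible but not certain.

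**Step 2: mucus rows, only women with discharge counted.** Numerator and denominator are then the same group, so no single-choice category exceeds 100%. The table would, however, leave out 152 − 30 = 122 of 152 women at d = 20%, and 152 − 61 = 91 at d = 40%. The shell does not say which count is meant; neither one summarizes mucus among the women assessed.

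**Step 3: discharge rows.** Assume discharge in 61 of 152 (40.1%) on LACTIN-V and 15 of 76 (19.7%) on placebo, and profuse discharge in 15 and 4 women. The shell prints 15/61 = 25% and 4/15 = 27%. Over women examined, the figures are 15/152 = 9.9% and 4/76 = 5.3%. Both are valid summaries. The first describes discharge once present; only the second shows how often profuse discharge was seen, and the shell has no line for that kind of figure or for 40.1% against 19.7%.

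**Step 4: visits.** The shell ends at Visit 4 (Week 12). Protocol 7.8 and the schedule of events place a pelvic examination at Visit 7 (Week 24). The SAP gives no reason for leaving it out.

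**The case against.** Several points on the other side stand.

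- A reader might infer that the arms would look identical however common discharge is. The shell does not support that. It prints n beside each percentage, and in Step 3 the profuse row shows 15 against 4. SAP 6.1 adds: "The total population size relevant to that table/column if applicable, including any missing observations will be displayed in the tables". If the visit N meant women examined, the frequency could be worked out from the source counts. What remains is that this N is undefined and no frequency is printed.
- A reader might also infer that discharge is nowhere compared between arms. It is. Abnormal vaginal discharge is a solicited event. Table 108 gives it by arm with Blaker intervals, Table 110 by maximum severity, and Tables 115-118 by arm and week through Week 24. These are memory-aid reports, and Table 108 counts treatment-emergent events, so they do not replace the examination finding.
- Clinician-observed discharge can also reach the adverse event tables, because Protocol Appendix B grades it. The same appendix keeps only the more severe of the history and examination grades, so that route gives no examination frequency by visit.
- The tables are meant to describe characteristics, and for the discharge block the conditional denominator does that correctly.
- Values above 100% need mucus counts that include women without discharge. Listing 33 suggests this, but the shell does not state it.

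**Conclusion.** The point holds in a narrow form. For the mucus block, the stated denominator is the wrong group under either way of counting: percentages can exceed 100%, or women without discharge disappear from the summary. This rests on the single footnote and on the absence of a discharge condition in Listing 33, not on the assumed rates. The undefined visit N, the missing frequency row and the missing Visit 7 column are gaps in the same shell.

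The importance is minor. The tables are descriptive, no hypothesis test depends on them, and the subject-level data are listed. The documents do not support a claim that the plan conceals how often discharge occurs; what is missing is the clinician-observed frequency by visit.

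**What to change.** In the shell for Tables 133-135:

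1. Use women with cervical mucus assessed at the visit as the denominator for the mucus rows.
2. Define the visit N as women with a pelvic examination at that visit.
3. Add a row for abnormal discharge present, over that N, with a Blaker interval per arm, as SAP 6.1 sets for safety proportions.
4. Keep the current footnote for the discharge characteristics only.
5. Add a Visit 7 column.

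The cost is footnote and shell edits plus the matching programming. The items are already in Listings 32 and 33, so no new data collection is needed.

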Figure 41: Maximum Severity of Solicited Local Adverse Events by Symptom and Treatment Group - Safety Population	142
Figure 42: Maximum Severity of Solicited Systemic Adverse Events by Symptom and Treatment Group - Safety Population	143
Figure 43: Maximum Severity of Solicited Local Adverse Events by Day and Treatment Group—Safety Population	144
Figure 44: Maximum Severity of Solicited Systemic Adverse Events by Day and Treatment Group—Safety Population	144
Figure 45: Frequency of Adverse Events by MedDRA System Organ Class and Severity	145
Figure 46: Incidence of Adverse Events by MedDRA System Organ Class and Maximum Severity	146
Figure 47: Frequency of Adverse Events by MedDRA System Organ Class and Relationship to Treatment.....	147
Figure 48: Incidence of Adverse Events by MedDRA System Organ Class and Relationship to Treatment.....	148

Figure 1: CONSORT Flow Diagram

Implementation notes: The actual diagram will match the design of this study.

[figure not shown]

Figure 2: Time to BV Recurrence by Visit 4 (Week 12) by Treatment Group

[figure not shown]

Figure will be a 2x2 panel plot with each panel displaying one of the analysis populations: ITT, mITT, CC, and PP.

[figure not shown]
Figures with similar format:

Figure 3: Time to BV Recurrence by Visit 7 (Week 24) by Treatment Group

Figure 4: Time to *L. crispatus* Colonization by Visit 4 (Week 12) by Treatment Group

Figure 5: Time to *L. crispatus* Colonization by Visit 7 (Week 24) by Treatment Group

[figure not shown]
Figure 6: *L. crispatus* CTV-05 Concentration by Time Since Last Dose, Week, and Treatment Group-ITT Population

Figures with similar format:

- Figure 7:** *L. crispatus* CTV-05 Concentration by Time Since Last Dose, Week, and Treatment Group-mITT Population
- Figure 8:** *L. crispatus* CTV-05 Concentration by Time Since Last Dose, Week, and Treatment Group-CC Population
- Figure 9:** *L. crispatus* CTV-05 Concentration by Time Since Last Dose, Week, and Treatment Group-PP Population
- Figure 10:** *L. crispatus* CTV-05 Concentration by Number of Condom-less Sexual Intercourse Acts, Week, and Treatment Group-ITT Population
- Figure 11:** *L. crispatus* CTV-05 Concentration by Number of Condom-less Sexual Intercourse Acts, Week, and Treatment Group-mITT Population
- Figure 12:** *L. crispatus* CTV-05 Concentration by Number of Condom-less Sexual Intercourse Acts, Week, and Treatment Group-CC Population
- Figure 13:** *L. crispatus* CTV-05 Concentration by Number of Condom-less Sexual Intercourse Acts, Week, and Treatment Group-PP Population
- Figure 14:** *L. crispatus* CTV-05 Concentration by Number of Partners, Week, and Treatment Group-ITT Population
- Figure 15:** *L. crispatus* CTV-05 Concentration by Number of Partners, Week, and Treatment Group-mITT Population
- Figure 16:** *L. crispatus* CTV-05 Concentration by Number of Partners, Week, and Treatment Group-CC Population
- Figure 17:** *L. crispatus* CTV-05 Concentration by Number of Partners, Week, and Treatment Group-PP Population

Figure 18: *L. crispatus* CTV-05 Concentration by Compliance Status, Week, and Treatment Group-ITT Population

[figure not shown]

Figures with similar format:

Figure 19: *L. crispatus* CTV-05 Concentration by Compliance Status, Week, and Treatment Group-mITT Population

Figure 20: *L. crispatus* CTV-05 Concentration by Compliance Status, Week, and Treatment Group-CC Population

Figure 21: *L. crispatus* CTV-05 Concentration by Day Since Last Day of Last Menstrual Period, Week, and Treatment Group - ITT Population

Implementation Note:

X-axis labels will read “Days Since Last Day of Last Menstrual Period”

[figure not shown]
Figures with similar format:

Figure 22: *L. crispatus* CTV-05 Concentration by Day Since Last Day of Last Menstrual Period, Week, and Treatment Group - mITT Population

Figure 23: *L. crispatus* CTV-05 Concentration by Day Since Last Day of Last Menstrual Period, Week, and Treatment Group - CC Population

Figure 24: *L. crispatus* CTV-05 Concentration by Day Since Last Day of Last Menstrual Period, Week, and Treatment Group - PP Population

Figure 25: *L. crispatus* CTV-05 Concentration by Menses After Last Dose Taken, Week, and Treatment Group-ITT Population

Implementation Note:

X-axis groups will be “Menses” and “No Menses”

[figure not shown]
Figures with similar format:

Figure 26: *L. crispatus* CTV-05 Concentration by Menses After Last Dose Taken, Week, and Treatment Group-mITT Population

Figure 27: *L. crispatus* CTV-05 Concentration by Menses After Last Dose Taken, Week, and Treatment Group-CC Population

Figure 28: *L. crispatus* CTV-05 Concentration by Menses After Last Dose Taken, Week, and Treatment Group-PP Population

Figure 29: CTV-05 Concentration by *L. crispatus* Concentration, Week, and Treatment Group - ITT Population

Implementation Note:

Y-axis labels will read “CTV-05 concentration”, X-axis labels will read “*L. crispatus* concentration”.

[figure not shown]
Figures with similar format:

Figure 30: CTV-05 Concentration by *L. crispatus* Concentration, Week, and Treatment Group - mITT Population

Figure 31: CTV-05 Concentration by *L. crispatus* Concentration, Week, and Treatment Group - CC Population

Figure 32: CTV-05 Concentration by *L. crispatus* Concentration, Week, and Treatment Group - PP Population

Figure 33: *L. crispatus* CTV-05 Concentration by Amsel Criteria, Week, and Treatment Group-ITT Population

Implementation Note:

X-axis groups will be “Positive” and “Negative”

Figures with similar format:

Figure 34: *L. crispatus* CTV-05 Concentration by Amsel Criteria, Week, and Treatment Group-mITT Population

Figure 35: *L. crispatus* CTV-05 Concentration by Amsel Criteria, Week, and Treatment Group-CC Population

Figure 36: *L. crispatus* CTV-05 Concentration by Amsel Criteria, Week, and Treatment Group-PP Population

Figure 37: *L. crispatus* CTV-05 Concentration by Nugent Score, Week, and Treatment Group-ITT Population

Figure 38: *L. crispatus* CTV-05 Concentration by Nugent Score, Week, and Treatment Group-mITT Population

Figure 39: *L. crispatus* CTV-05 Concentration by Nugent Score, Week, and Treatment Group-CC Population

Figure 40: *L. crispatus* CTV-05 Concentration by Nugent Score, Week, and Treatment Group-PP Population

Figure 41: Maximum Severity of Solicited Local Adverse Events by Symptom and Treatment Group - Safety Population

[figure not shown]

Figure 42: Maximum Severity of Solicited Systemic Adverse Events by Symptom and Treatment Group - Safety Population

[figure not shown]
[figure not shown]

[figure not shown]
Figure 43: Maximum Severity of Solicited Local Adverse Events by Day and Treatment Group— Safety Population

Figures with Similar Format:

Figure 44: Maximum Severity of Solicited Systemic Adverse Events by Day and Treatment Group— Safety Population

[figure not shown]
Figure 45: Frequency of Adverse Events by MedDRA System Organ Class and Severity

Implementation Note:

- Include “Any SOC” bars

[figure not shown]
Figure 46: Incidence of Adverse Events by MedDRA System Organ Class and Maximum Severity

Implementation Note:

- Include “Any SOC” bars

[figure not shown]
Figure 47: Frequency of Adverse Events by MedDRA System Organ Class and Relationship to Treatment

Implementation Note:

- Include “Any SOC” bars

Figure 48: Incidence of Adverse Events by MedDRA System Organ Class and Relationship to Treatment

Implementation Note:

- Include “Any SOC” bars

LACTIN-V/Placebo	LACTIN-V/Placebo	xxxxxx	[e.g., Safety, ITT, mITT, CC, PP]	[e.g., Safety, ITT, mITT, CC, PP, Visit x]	Yes/No	xxxxxx
LACTIN-V/Placebo	LACTIN-V/Placebo	xxxxxx	[e.g., Safety, ITT, mITT, CC, PP]	[e.g., Safety, ITT, mITT, CC, PP, Visit x]	Yes/No	xxxxxx
LACTIN-V/Placebo	LACTIN-V/Placebo	xxxxxx	[e.g., Safety, ITT, mITT, CC, PP]	[e.g., Safety, ITT, mITT, CC, PP, Visit x]	Yes/No	xxxxxx

Note: “Yes” in the “Results available” column indicates that available data were removed from the analysis. If “Yes” the population in which data were removed will be listed in parenthesis. “No” indicates that no data were available for inclusion in the analysis.

Implementation Notes:

1. Sort order will be actual treatment group, Subject ID
2. Reasons Subject Excluded should match the same verbiage that is used on the Analysis population tables
3. If all subjects received the correct treatment, only display “Treatment Group”.

Listing 2 Subjects Whose Assigned Treatment Group Does Not Match Their Randomized Treatment Group

Subject ID	Treatment Group at Randomization	Treatment Actually Received
xxxxxx	LACTIN-V/Placebo	LACTIN-V/Placebo
xxxxxx	LACTIN-V/Placebo	LACTIN-V/Placebo

Implementation Note:

1. Sort order is Subject ID.

Listing 3 Early Terminations or Discontinued Subjects-All Enrolled Subjects

Actual Treatment Group	Randomized Treatment Group	Subject ID	Category	Study Day Corresponding to Early Termination/Treatment Discontinuation/Completion	Reason for Early Termination/ Treatment Discontinuation
LACTIN-V/Placebo	LACTIN-V/Placebo	XXXXXXXX	Early Termination/Treatment Discontinuation/Completion	xx	XXXXXXXXXXXXXXXXXXXX
LACTIN-V/Placebo	LACTIN-V/Placebo	XXXXXXXX	Early Termination/Treatment Discontinuation/Completion	xx	---

Implementation Notes:

1. Sort order will be by Actual Treatment Group, Subject ID, Category
2. Category will be "Early Termination", "Completion" or "Treatment Discontinuation". If a subject discontinued treatment, they will have two records.
3. In the "Reason" column, concatenate any "specify" fields, including AE number and DV number.

Listing 4 Subject-Specific Protocol Deviations-All Enrolled Subjects

Deviation Number	Study Day	Deviation Description	Deviation Category	Reason for Deviation	Deviation Affected Product Stability?	Deviation Resulted in AE?	Deviation Resulted in Subject Termination?	Deviation Resolution	Comments
Actual Treatment Group: , Randomized Treatment Group: , Subject ID:									
xx	xx	xxxxxxx	xxxxxxxxxxx	xxxxxxx	Yes/No	Yes/No	Yes/No	Yes/No	xxxxxxxxxxx
xx	xx	xxxxxxx	xxxxxxxxxxx	xxxxxxx	Yes/No	Yes/No	Yes/No	Yes/No	--

Note: Deviation description column will contain all subfields concatenated together

Implementation Notes:

1. Sort order will be by Actual Treatment Group, Subject ID, Deviation Number
2. In the Deviation Category column concatenate any specify fields
3. In the Reason for Deviation column concatenate any specify fields.

Listing 5 Non-Subject-Specific Protocol Deviations

Site	Deviation	Start Day	End Day	Reason for Deviation	Deviation Resulted in Subject Termination?	Deviation Affected Product Stability?	Deviation Category	Deviation Resolution	Comments
xxxx	xxxx	xx	xx	xxxx	Yes/No	Yes/No/NA	xxxx	xxxx	xxxx
xxxx	xxxx	xx	xx	xxxx	Yes/No	Yes/No/NA	xxxx	xxxx	xxxx

Note: Deviation column will contain all subfields concatenated together

Implementation Notes:

1. Sort order will be by Site Name, Start Date
2. In the Deviation Category column concatenate any specify fields
3. In the Reason for Deviation column concatenate any specify fields.

Listing 6 Individual Efficacy Response Data

Study Day (Week)	Homogeneous, thin, grayish-white discharge	Vaginal pH	Amine (“whiff”) test on KOH wet mount	Clue Cells on wet mount (%)	Amsel Criteria	Nugent Score	BV Diagnosis	L. crispatus Concentration (copies/mL)	CTV-05 Concentration (copies/mL)	Lactobacillus spp. Concentration (copies/mL)	Total Bacteria Concentration (copies/mL)	L. crispatus Colonization Status
Actual Treatment Group: , Randomized Treatment Group: Subject ID:												
x (x)	Present/ Absent/ Not Assessed	xx.x	Negative/ Positive/ Not Assessed	xx	x	x	Positive/ Negative/ Indeterminate	x.x E x	x.x E x	x.x E x	x.x E x	Successful/ No colonization

Implementation Notes:

1. Sort order is actual treatment group, Subject ID, Study Day.
2. If all subjects received the correct treatment, only display “Treatment Group”.

Listing 7 Compliance Data- All Treated Subjects

Actual Treatment Group	Subject ID	Week	Dose	Dose Taken? (Subject Report)	Study Day of Administration (Subject Report)	Time of Administration (Subject Report)	Number of Applicators Returned (Used / Unused)	Staining Assessment (Used / Unused / Indeterminate)	Compliance Status
xxxxxx	xxxxxx	1	1	Yes/No	xx	xx:xx	x / x	x / x / x	Compliant/Non-compliant
			2	Yes/No	xx	xx:xx			
			3	Yes/No	xx	xx:xx			
			4	Yes/No	xx	xx:xx			
			5	Yes/No	xx	xx:xx			
		2	1	Yes/No	xx	xx:xx	x / x	x / x / x	
			2	Yes/No	xx	xx:xx			
		3	1	Yes/No	xx	xx:xx	x / x	x / x / x	
			2	Yes/No	xx	xx:xx			
		Etc.							

Implementation Notes:

- Sort order is actual treatment Group, Subject ID.
- Total number of doses is 25. Number of doses not taken will be calculated as 25 - Number of doses taken as scheduled - Number of doses taken out of window.
- If a subject does not have a record for 'Returned Used Applicators' or 'Returned Unused Applicators', then an 'Unknown' will be placed in those columns.

Listing 8 Missed Dose Data- All Treated Subjects

Actual Treatment Group	Randomized Treatment Group	Subject ID	Dose(s) Missed
LACTIN-V/Placebo	LACTIN-V/Placebo	xxxxxx	[e.g., Week 2 Dose 1, Week Dose 2, etc.]

Implementation Notes:

1. Sort order is Treatment Group, Subject ID.

Listing 9 Individual Acceptability Questionnaire Responses

Actual Treatment Group	Subject ID	Questionnaire Item	Questionnaire Sub-Item	Screening		Follow-up	
				Study Day (Week)	Response	Study Day (Week)	Response
LACTIN-V/Placebo	xxxxxx	1	-	x (x)	xxx	x (x)	xxx
		2	A	x (x)	Yes/No	x (x)	Yes/No
			B	x (x)	Yes/No	x (x)	Yes/No
			C	x (x)	Yes/No	x (x)	Yes/No
			D	x (x)	Yes/No	x (x)	Yes/No
			E	x (x)	Yes/No	x (x)	Yes/No
			F	x (x)	Yes/No	x (x)	Yes/No
		3	-	x (x)	xxx	x (x)	xxx
		4	-	x (x)	xxx	x (x)	xxx
		5	-	x (x)	xxx	x (x)	xxx
Etc.							

Implementation Notes:

1. Sort order is actual treatment group, Subject ID, Study Day.
2. If all subjects received the correct treatment, only display “Treatment Group”.

Listing 10 Demographic Data-All Enrolled Subjects

Actual Treatment Group	Randomized Treatment Group	Subject ID	Age at Enrollment (years)	Ethnicity	Race
LACTIN-V/Placebo	LACTIN-V/Placebo	xxxxxx	xx	xxxxxx	xxxxxx
LACTIN-V/Placebo	LACTIN-V/Placebo	xxxxxx	xx	xxxxxx	xxxxxx
LACTIN-V/Placebo	LACTIN-V/Placebo	xxxxxx	xx	xxxxxx	xxxxxx

Implementation Notes:

1. Sort order will be by Actual Treatment Group, Subject ID
2. For the Race column, if a subject is Multi-Racial, all races will be listed, separated by a comma

Listing 11 Screening Gynecological History Interview-All Enrolled Subjects

Study Day	Have you been amenorrheic for at least 3 months due to use of a long-acting progestin or continuous use of oral contraceptives?	First Day of your last menstrual period (Study Day)	How many days is your average menstrual cycle?	How many days does your period last?	In the past 3 months, have you had any abnormal menstrual cycles?	What sanitary products do you use during your period?	Have you ever douched or used vaginal preparations or drying agents?	In the last 30 days how many times have you douched or used vaginal preparations or drying agents?
Actual Treatment Group: , Randomized Treatment Group: Subject ID:								
xx	Yes/No	xx	xx	xx	Yes/No [cycle length less than 21 days/cycle length more than 35 days/Intermenstrual bleeding/spotting]	Pads/Cups/Tampons/Other	Yes/No [Specify]	xx/NA

Implementation Notes:

- Sort order will be by Actual treatment group, Subject ID
- For questions that are parented, if the parent question is “No” and the subsequent fields are not required, fill the cell with “—“
- Includes data from Visit 00
- If answer to ‘In the past 3 months, have you had any abnormal menstrual cycles?’ is “Yes,” then concatenate the answer to the abnormal cycles that were experienced
- If answer to ‘Have you ever douched or used vaginal preparations or drying agents?’ is “Yes,” then concatenate answer to the ‘specify’ field. If the answer is “No” then there will be no answer.

Listing 12 Screening Sexual History Interview-All Enrolled Subjects

Study Day	How many male partners have you had in the past 6 months?	How many female partners have you had in the past 6 months?	Have you had sex in the past 30 days?	How many times did you have sex?	How many times did you have protected sex?	How many times did you have unprotected sex?	How many days has it been since the last time you had sex?
Actual Treatment Group: , Randomized Treatment Group: Subject ID:							
xx	xx	xx	Yes/No	xx	xx	xx	xx

Implementation Notes:

1. Sort order will be by actual treatment group, Subject ID
2. For questions that are parented, if the parent question is “No” and the subsequent fields are not required, fill the cell with “—“
3. Includes data from Visit 00

Listing 13 Follow-up Gynecological History Interview-All Enrolled Subjects

Study Day	Have you menstruated since your last visit?	First Day of your last menstrual period (Study Day)	Since your last visit, have you experienced any spotting or bleeding other than menstrual bleeding?	Since your last visit, have you used scented tampons?	Since your last visit, have you douched or vaginally inserted anything other than the study applicator or MetroGel?	How many days has it been since you last douched or vaginally inserted anything other than the study applicator or MetroGel?	Since your last visit, how many times have you douched or vaginally inserted anything other than the study applicator or MetroGel?	Have you changed birth control methods or started a new method since the last visit?
Actual Treatment Group: , Randomized Treatment Group: Subject ID:								
xx	Yes/No	xx	Yes/No	Yes/No/NA	Yes/No [specify]	xx	xx	Yes/No/NA

Implementation Notes:

- Sort order will be by actual treatment group, subject ID
- For questions that are parented, if the parent question is “No” and the subsequent fields are not required, fill the cell with “—“
- Includes data from Visit 0, 02, 03, 04,07
- If answer to ‘Since your last visit, have you douched or vaginally inserted anything other than the study applicator or MetroGel?’ is “Yes,” concatenate answer to ‘Specify’ field. If the answer is “No” then there will be no answer.

Listing 14 Follow-up Sexual History Interview-All Enrolled Subjects

Study Day	Have you had sex since the last visit?	How many times did you have sex?	How many new partners did you have?	How many days has it been since the last time you had sex?	If you had sex with a man, did your partner use a condom each time?
Actual Treatment Group: , Randomized Treatment Group: Subject ID:					
xx	Yes/No	xx	xx	xx	Yes/No/NA

Implementation Notes:

1. Sort order will be by Subject ID
2. For questions that are parented, if the parent question is “No” and the subsequent fields are not required, fill the cell with “—“
3. Includes data from Visit 0, 02, 03, 04,07

Listing 15 Screening Pregnancy History Interview-All Enrolled Subjects

Study Day	How many times have you been pregnant?	Number of Live Births	Number of Stillborn Births	Number of Spontaneous Abortions	Number of Elective Abortions	Number of Ectopic Pregnancies	Do you have any children born with congenital anomalies?	What is your current Relationship Status?
Actual Treatment Group: , Randomized Treatment Group: Subject ID:								
xx	xx	xx	xx	xx	xx	xx	Yes/No [Specify]	Married/Divorced/Separated/Single (never married)/Widowed/Steeds partner, cohabitating/Steady partner, not cohabitating/Casual partner

Implementation Notes:

- Sort order will be by Actual treatment group, Subject ID
- For questions that are parented, if the parent question is “No” and the subsequent fields are not required, fill the cell with “—“
- Includes data from Visit 00
- If answer to ‘Do you have any children born with congenital anomalies?’ is yes, then concatenate answer to ‘Describe.’ If the answer is “No” then there will be no answer.

Listing 16 Pre-Existing Medical Conditions- All Enrolled Subjects

Actual Treatment Group	Randomized Treatment Group	Subject ID	MH Number	Medical History Term	Condition Start Day	Condition End Day	MedDRA System Organ Class	MedDRA Preferred Term
LACTIN-V/Placebo	LACTIN-V/Placebo	xxxxxx	xxx	xxxxxx	xx	xx	xxxxxx	xxxxxx
LACTIN-V/Placebo	LACTIN-V/Placebo	xxxxxx	xxx	xxxxxx	xx	xx	xxxxxx	xxxxxx

Implementation Notes:

- Sort order is Actual Treatment Group, Subject ID, MH Number.
- "Condition Start Day" and "Condition End Day" are relative to enrollment (which is Day 1, day before enrollment is Day -1). Rather than use exact study days, categorize as follows:
 - > 5 years prior to enrollment
 - 1-5 years prior to enrollment
 - 1-12 months prior to enrollment
 - Within 1 month of enrollment
 - During Study
 - If Ongoing at the end of the study, display "Ongoing" in the "Condition End Day" column.
 - If ending is unknown at the end of the study, display "Unknown" in the "Condition End Day" column.

Listing 17 Concomitant Medications

Actual Treatment Group	Randomized Treatment Group	Subject ID	Concomitant Medication Number	Medication	Medication Start Day	Medication End Day	Indication	Taken for an AE? (AE Description; AE Number)	Taken for a condition on Medical History? (MH Description; MH Number)
LACTIN-V/Placebo	LACTIN-V/Placebo	LACTIN-V/Placebo	xx	xxxxxx	xx	xx	xxxxxx	Yes/No xxxxx; xx	Yes/No xxxxx; xx
LACTIN-V/Placebo	LACTIN-V/Placebo	LACTIN-V/Placebo	xx	xxxxxx	xx	xx	xxxxxx	Yes/No xxxxx; xx	Yes/No xxxxx; xx

Implementation Notes:

- Sort order is actual treatment group, Subject ID, concomitant medication number.
- 'Medication Start Day' and 'Medication End Day' are relative to enrollment (which is Day 1, day before enrollment is Day -1). For medication start dates that are > 30 days prior to enrollment, rather than use exact days, categorize as follows:
 - > 5 years prior to enrollment
 - 1- 5 years prior to enrollment
 - 1-12 months prior to enrollment.
 - For 'Medication End Day', if medication is Ongoing, display 'Ongoing' in the 'Medication End Day' column.
 - For 'Medication End Day', if end of medication is unknown, display 'Unknown' in the 'Medication End Day' column.
- If a Medication is taken for an AE, then concatenate the conmed with the Advere Events by AENUM and report the AETERM, plus the AE Number.
- If a Medication is taken for an MH, then concatenate the conmed with the Medical History event by MHNUM and report the MHTERM, plus the MH Number.
- Include the birth control information in this dataset. The birth control information is coming from the RP/SUPPRP or BC1 dataset.
- If all subjects received the correct treatment, only display "Treatment Group".

Listing 18 Solicited Local Events –All Treated Subjects

Week	Study Day	Vaginal Bleeding Other than Menstruation	Abnormal Vaginal Discharge	Abnormal Vaginal Odor	Genital Itching	Genital Burning	External Genital Irritation	External Genital Swelling	Genital Rash
Actual Treatment Group: , Randomized Treatment Group: Subject ID:									
x	x	[severity]	[severity]	[severity]	[severity]	[severity]	[severity]	[severity]	[severity]
x	x	[severity]	[severity]	[severity]	[severity]	[severity]	[severity]	[severity]	[severity]

Implementation Notes:

- Sort order is actual treatment group, Subject ID, Study Day.
- If a symptom is ongoing after day 5, add a row for Day 6 and for each day until the end date of the symptom. The severity will be the maximum severity reported for that symptom.
- Mark all severities with a +, that are considered treatment emergent solicited adverse events.
- Severity will be color coded
- If all subjects received the correct treatment, only display “Treatment Group”.

Listing 19 Solicited Systemic Events – Safety Population

Week	Study Day	Nausea*	Vomiting*	Abdominal Pain/Cramps*	Diarrhea*	Constipation*	Pain/Burning with Urination	Frequent Urination	Blood in Urine*	Headache*
Actual Treatment Group: , Randomized Treatment Group: Subject ID:										
x	x	[severity]	[severity]	[severity]	[severity]	[severity]	[severity]	[severity]	[severity]	[severity]
x	x	[severity]	[severity]	[severity]	[severity]	[severity]	[severity]	[severity]	[severity]	[severity]
Note: *Symptom not collected during weeks 12-24.										

Implementation Notes:

- Sort order is actual treatment group, Subject ID, Study Day.
